Subjects will be recruited via Flyers posted on Campus and/or in Obstetrics and Gynecology practices and/or via ads posted on Craigslist by research coordinator, [name]. From these ads, interested individuals will be asked to go on Survey Monkey (<https://www.surveymonkey.com/r/HPENlabresearch>) and complete a survey that will help us determine whether they meet our selection criteria or email [name] at [[contact]](mailto:[contact]) or call the research team. Research coordinator will then contact individuals who may meet selection criteria. She and [name] and/or [name] will meet with them and give them the informed consent to read and go through it with the subjects. Upon receipt of a signed informed consent, participants will meet with [name] or [name] who will diagnose them with HSDD. If the subject does not have HSDD, she is not eligible to participate in the study. Subjects with a confirmed diagnosis of HSDD by [name] or [name] will then be randomly assigned by the UChicago Pharmacy/Investigational Drug Service to either Addyi (100 mg once daily at bedtime for 8 weeks, n = 60 subjects) or placebo (100 mg once daily at bedtime for 8 weeks, n = 60 subjects). The research question of this double-blind randomized outpatient clinical trial is to determine the pre-post change in the Flibanserin group and investigate the

extent to which Flibanserin normalizes brain activity in women with HSDD and the extent to which regional brain activation is associated with changes in symptoms and behavior (as measured with self-report measures of sexual desire and/or eye-tracking movements).

The study is registered on clinicaltrials.gov.

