## **6. Duration of Protocol:**

The total duration of the entire study on campus is 4.5 hours maximum. **Visit 1's duration:** 2 hours. Upon receipt of the subject's written consent, the subject will meet with [name] or [name] to have a diagnosis of HSDD confirmed, take a urine pregnancy test, and be asked to fill out questionnaires (duration 45 minutes maximum). Then, an IRB-approved member of the HPEN laboratory will walk the subject to the laboratory where the subject will be completing other questionnaires and performing the behavioral visual task while the subject's brain activity and eye movements are recorded (1h15 minutes maximum, including breaks and time to walk to the laboratory). At the end of Visit 1, a member of the HPEN laboratory will walk the subject to the pharmacy where they will receive either Flibanserin or Placebo. The HPEN member will not know what the patient receives (placebo or Flibanserin). One week after visit 1, a member of the study staff will contact the subject via telephone to see if the subject has experienced any side effects or if the subject has any questions. If any side effects are reported, the study staff will immediately contact [name] or [name] to confirm that any appropriate follow up is provided. **Phone call 2's duration:** 30 minutes. Two weeks after visit 1, the subject will be asked about any side effects she has experienced or is currently experiencing. The subject will also be asked to fill out some of the same questionnaires as visit 1 and answer questions about mood and sexual desire. **Visit 2's duration:** 1 hour. The subject will go directly to the HPEN laboratory, where the subject will perform the behavioral visual task again while the subject's brain activity and eye movements are recorded and fill out the same questionnaires the subject filled out during Visit 1. **Visit 3's duration:** 1 hour. The subject will again go directly to the HPEN laboratory to perform the behavioral visual task while the subject's brain activity and eye movements are recorded and fill out the same questionnaires as Visits 1 and 3.

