Median effective doses of flibanserin on increase in SD level will demonstrate at least a medium effect size (e.g., Cohen's  $d > 0.48$ ) relative to placebo (PBO); and at least a medium effect size (Cohen's  $d > 0.48$ ) between flibanserin and PBO conditions in SD levels; and relationship between change in SD self-report levels and change in behavioral responses (reaction times) during SD paradigm in flibanserin (vs PBO) is of at least a medium effect size ( $r > 0.48$ ); or relationship between change in flibanserin and change in electrophysiological responses during SD paradigms in flibanserin (vs. PBO) is of at least a medium effect size ( $r > 0.48$ ); Relationship between change in Flibanserin and change in eye movement responses during SD paradigms in Flibanserin(vs. PBO) is of at least a medium effect size ( $r > 0.48$ ). There will be no adverse events of more than mild severity which are rated as possibly, probably, or definitely related to acute, oral administration of flibanserin to a greater extent than PBO in HSDD participants.

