### **Most Common Adverse Reactions**

Table 2 summarizes the most common adverse reactions reported in four trials of premenopausal women with HSDD. This table shows adverse reactions reported in at least 2% of patients treated with ADDYI and at a higher incidence than with placebo [see **WARNINGS AND PRECAUTIONS**]. The majority of these adverse reactions began within the first 14 days of treatment.

**Table 2: Common Adverse Reactions\* in Randomized, Double-blind, Placebo-controlled Trials in Premenopausal Women with HSDD**

	PLACEBO (N=1556)	ADDYI (N=1543)
Dizziness	2.2%	11.4%
Somnolence	2.9%	11.2%
Nausea	3.9%	10.4%
Fatigue	5.5%	9.2%
Insomnia	2.8%	4.9%
Dry mouth	1.0%	2.4%

\* Adverse reactions reported in ≥ 2% of patients receiving 100 mg ADDYI at bedtime and at a higher incidence than placebo-treated patients.

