**25. Study Drug Dispensation:**

During the first visit, after [name] or [name] meet with the subject and determine if the subject is eligible to participate in the study, one of them will send a prescription to the investigational drug services (IDS) pharmacy at the University of Chicago Medical Center. The prescription is based on a randomization chart, so the physicians will order the drug by placing a coded patient number on the prescription sheet. When sent to the IDS pharmacy, they will know if that specific ID number is randomized to the flibanserin or the placebo, thus keeping it blinded to the physicians. Shortly after the study drug is ordered, a member of the study staff will pick it up from the IDS pharmacy and deliver it to the EEG lab where the subject will be doing the EEG procedures. After the subject is finished with all visit procedures, she will be given the study drug and instructions on how to take it.

All tablets will be dispensed at one time during the first visit. The total number of tablets each subject will receive is 56 tablets (8 weeks x 1 tablet/day).

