## **28. Adverse Events:**

[name], [name], and [name] will be responsible for the detection, documentation, classification, reporting, and follow-up of adverse events, including events meeting the definition of a serious adverse event (SAE). An adverse event (AE) us any undesirable experience associated with the use of a medical product in a patient. For the regulatory definitions of SAEs, refer to

<http://www.fda.gov/Safety/MedWatch/HowToReport/ucm053087.htm>.

All AEs will be recorded regardless of causality or severity. At the minimum, information collected concerning AEs should include the following: onset date, resolution date, severity (i.e., mild, moderate, or severe), relationship to study drug, intervention (if needed), seriousness of the event, and outcome.

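### The safety criterion in Section 11 is tied to undefined *acute* administration, which does not fit 8 weeks of nightly dosing or the relationship field in Section 28

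*Combined protocol and SAP*

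**What the plan says.** The clause closes the list of expectations under Statistical Hypotheses in Section 11. It opens "There will be no adverse events of more than mild severity" and then limits the events to those rated possibly, probably or "definitely related to acute, oral administration of flibanserin to a greater extent than PBO in HSDD participants". It gives no meaning for *acute*, no onset window and no cut-off day.

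The treatment is repeated dosing. Section 5 assigns women to "Addyi (100 mg once daily at bedtime for 8 weeks, n = 60 subjects" or to placebo on the same schedule. Section 25 adds: "The total number of tablets each subject will receive is 56 tablets (8 weeks x 1 tablet/day". The hypotheses in Section 3 also concern an 8-week intake.

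Section 28 governs collection: "All AEs will be recorded regardless of causality or severity". Its minimum data set includes onset date and "severity (i.e., mild, moderate, or severe), relationship to study drug", and it draws no line between acute and repeated dosing.

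**The concern.** A safety criterion should refer to the exposure that the trial gives and should be answerable from the data that the trial collects. This one refers to a kind of administration that appears nowhere else in the plan. Someone applying it must decide, event by event and without a rule, whether a reaction belongs to acute administration or to the course as a whole.

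At stake is the one stated drug-placebo comparison of adverse events. Half the planned sample (60 of 120) is postmenopausal, a group for whom Section 5 says the drug is not FDA approved, and the safety data reproduced in Section 12 come from premenopausal women. If events attributed to repeated dosing are set aside, the criterion could be reported as met without addressing the whole course of treatment.

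**Working it through.** The question is one of wording, so the main check is to compare sections. One figure can be reproduced first.

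1. Exposure. Inputs from Section 25: 8 weeks, 1 tablet per day. 8 × 7 × 1 = 56 tablets, which matches the stated total. No arm, visit or challenge in the text available for this review uses a single or acute dose. Sections 7 and 19 were not in that text, and nothing is concluded about them.

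2. Each element of the Section 11 clause against the Section 28 record:

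| Element of the clause | Matching item in Section 28 |
|---|---|
| Worse than mild | Severity: mild, moderate or severe |
| Possibly, probably or definitely related | Relationship to study drug |
| Related to *acute* administration | None |
| More than on placebo | Not a field; follows from the randomised arm |

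Only the acute element has no counterpart. In the other direction, Section 28 collects onset date, which the clause does not use.

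3. What the word changes. Take a hypothetical moderate event in week 6, rated probably related to study drug.

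- If the rater attributes it to the previous night's tablet, it can count even with the word *acute* in place.
- If the rater attributes it to several weeks of dosing, it counts when the standard is relationship to study drug, but can be left out when the standard is relationship to acute administration.

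Severity, relatedness grade and onset date are the same in both cases. Only the reading of an undefined word differs.

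4. Size. Measuring the effect would need the share of more-than-mild, related events that raters would attribute to repeated rather than acute dosing, in each arm over 8 weeks. The documents do not give it. No sample-size or power figure depends on this clause.

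**The case against.** The strongest defence is that this is a loose word with little consequence. The sentence is phrased as a prediction within a list of expected effects. Safety is not among the outcome measures in Section 4, and no decision or stopping rule in the available text depends on the sentence. All events are recorded with onset date, severity and relationship to study drug, so late events can still be seen and reported by arm. All of this stands, and it is why the point is minor. It does not make the criterion fit the design.

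Three stronger readings are tempting, and the documents support none of them.

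- A reader might infer that events starting later in treatment necessarily fall outside the criterion. The text does not say so. *Acute* describes the administration, not the time of onset, and neither Section 11 nor Section 28 sets a window. Section 6 has an early contact ("Two weeks after visit 1, the subject will be asked about any side effects she has experienced or is currently experiencing") and Section 12 says of the earlier trials "The majority of these adverse reactions began within the first 14 days of treatment", but neither statement defines *acute*.
- A reader might cite the sedation-related injuries in Section 12 as events that would be missed. Those injuries had CNS-depression reactions reported in the preceding 24 hours. That short interval could readily be linked to a recent dose, so the example points the other way.
- A reader might size the loss from Table 2 in Section 12. That table covers 24-week trials, so later onsets there can fall in the 24 − 8 = 16 weeks that this trial does not have. It includes all severities and is not limited to events rated related. Any day-14 cut-off would be the reader's own assumption.

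**Conclusion.** Wrong as written; minor severity. The Section 11 criterion names a form of exposure that the trial does not use, leaves it undefined, and does not match the relationship field in Section 28. It can be read to leave out more-than-mild events attributed to repeated or cumulative dosing.

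The conclusion rests on the ordinary meaning of *acute* and on the absence of a definition in the available text. It does not assume any rate of late events, and no number of affected events can be given. The effect is on how the safety statement is judged, not on what is recorded.

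**What to change.** In the safety clause of Section 11, replace the words running from *acute* to *flibanserin* with *study drug, with onset from the first dose to the Visit 3 (week 8) assessment*. Then tabulate by arm, for that whole period, the events that meet the criterion. If *acute* was intended, the alternative is to define it and say how other related events enter the safety conclusion.

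The cost is one phrase and one table. The Section 28 data set already includes onset date, severity and relationship, so no new item is needed. The only downside is that more events may count against the criterion. The change does not make the criterion as broad as Section 28: the severity and relatedness filters remain, so mild and unrelated events are recorded but still not judged here.

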## **12. Potential Risks and Benefits:**

The study will offer no direct benefits (besides monetary benefits and potential improvement of sexual desire) to participants. The questionnaires, tracking eye-movement, and EEG behavioral task also present minimal risks, which may include boredom and fatigue from looking at pictures for a few minutes during EEG collection and anxiety or discomfort or distress related to responding to questionnaires.

Addyi risks: Addyi (flibanserin) is a multifunctional serotonin agonist and antagonist (MSAA) indicated for the treatment of premenopausal women with acquired, generalized hypoactive sexual desire disorder (HSDD) as characterized by low sexual

desire that causes marked distress or interpersonal difficulty and is NOT due to: a co-existing medical or psychiatric condition, problems within the relationship, or the effects of a medication or other drug substance. The recommended dosage of Addyi is 100 mg taken once daily at bedtime.

**CONTRAINdications:** Alcohol; Moderate or strong cytochrome P450 3A4 inhibitors; Hepatic impairment.

IF THE SUBJECTS ARE A NURSING MOTHER, THEIR PARTICIPATION IS NOT RECOMMENDED.

IF THE SUBJECTS ARE PREGNANT, YOUR PARTICIPATION CANNOT BE ACCEPTED.

**DRUG INTERACTIONS:** Oral contraceptives increase Flibanserin exposures and incidence of adverse effects.

FDA-approved Flibanserin has known side effects we want you to be aware of, such as syncope and Central Nervous System (CNS) depression.

**Other common side effects of Addyi (Flibanserin) include:** dizziness, sleepiness, nausea, fatigue, insomnia, and dry mouth. Other side effects of Addyi include anxiety, constipation, abdominal pain, menstrual spotting, rash, sedation, and spinning sensation (vertigo).

**Addyi may interact with alcohol, CNS depressants (such as diphenhydramine, opioids, hypnotics, benzodiazepines), antifungals, antiviral drugs, grapefruit juice, oral contraceptives, cimetidine, fluoxetine, ginkgo, ranitidine, proton pump inhibitors, selective serotonin reuptake inhibitors (SSRIs), some antibiotics, nefazodone, , ketoconazole, itraconazole, posaconazole, clarithromycin, ritonavir, saquinavir, nelfinavir, indinavir, boceprevir, telaprevir, telithromycin, conivaptan, amprenavir,**

atazanavir, ciprofloxacin, diltiazem, erythromycin, fluconazole, fosamprenavir, verapamil, paroxetine, carbamazepine, phenobarbital, phenytoin, rifabutin, rifampin, rifapentine, St. Johns Wort, digoxin, sirolimus, and some medicines used to treat high blood pressure, chest pain (angina), or other heart problems.

Drug interactions can be found in all tables including CYP3A4 inhibitors and CYP2C19 on:

<http://www.fda.gov/Drugs/DevelopmentApprovalProcess/DevelopmentResources/DrugInteractionsLabeling/ucm093664.htm>

Note: The use of moderate or strong CYP3A4 inhibitors is contraindicated in patients taking flibanserin, and flibanserin may interact with other medications (weak CYP3A4 inhibitors, strong CYP2C19 inhibitors, CYP3A4 inducers, and digoxin).

**Addyi is only available through the Addyi risk evaluation and mitigation strategy (REMS) Program because of the increased risk of severe low blood pressure and fainting (loss of consciousness) with alcohol use. By agreeing to participate in the present study and by signing the present consent form, the subject also agrees NOT to drink alcohol or beverages including alcohol while taking Addyi (Flibanserin), that is for a period of 8 weeks.**

If the subject feels that they won't be able to follow a non-alcoholic diet for 8 weeks, they will be asked to tell the research team. We will compensate them for their time spent with us.

***Data from Five 24-Week, Randomized, Double-Blind Placebo-Controlled Trials in Premenopausal Women with HSDD***

The data presented below are derived from five 24-week randomized, double-blind, placebo-controlled trials in premenopausal women with acquired, generalized HSDD. In these five trials, the frequency and quantity of alcohol use was not recorded. Three of these trials (Studies 1 through 3) also provided efficacy data [see **Clinical Studies**]. One of these trials (Study 5) did not evaluate the 100 mg bedtime dose.

In four trials, 100 mg ADDYI at bedtime was administered to 1543 premenopausal women with HSDD, of whom 1060 completed 24 weeks of treatment. The clinical trial population was generally healthy without significant comorbid medical conditions or concomitant medications. The age range was 18-56 years old with a mean age of 36 years old, and 88% were Caucasian and 9% were Black.

Serious adverse reactions were reported in 0.9% and 0.5% of ADDYI-treated patients and placebo-treated patients, respectively.

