### **5. Methodology:**

The proposed study aims to test 60 pre-menopausal heterosexual or bisexual women (i.e., women who are menstruating) and 60 postmenopausal heterosexual or bisexual women (women who are no longer menstruating for at least 6 months) with hypoactive sexual desire disorder (HSDD) and investigate how their brain activity (as measured by non-invasive surface electroencephalogram, EEG) responds to desirable stimuli (photographs of models in business suits) before and after the administration of an FDA approved drug, Addyi (ingredient Flibanserin, NDA# 022526) for sexual desire disorder. The goal of this experiment is to investigate how the subjects' brain waves and their subjective desire for sexual activity change after an 8-week intake of Addyi

(Flibanserin; 100mg **at bedtime**)—an FDA approved drug for the treatment of hypoactive sexual desire disorder (HSDD) in **premenopausal women (but not FDA approved in postmenopausal women)** or after an 8-week intake of a placebo. The pharmacist will randomly assign once the subject to the treatment group (group with Flibanserin) or to the control group (group with placebo). Before and then again after the 8-week regimen, the patient will be asked to fill-out a series of questionnaires (e.g., demographics, body image; sexual desire) and do a behavioral visual task on a computer while the patient's brain activity (brain waves) and eye-movement will be recorded using a non-invasive high-density electroencephalogram (EEG) system and a non-invasive eye-tracking system, respectively. At mid-term (at 4 weeks), the patient will be also asked to fill-out the same series of questionnaires (e.g., demographics, body image; sexual desire) and do the same behavioral visual task on a computer while the patient's brain activity (brain waves) and eye-movement will be recorded using a non-invasive high-density electroencephalogram (EEG) system and a non-invasive eye-tracking system, respectively.

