### **Adverse Reactions Leading to Discontinuation**

The discontinuation rate due to adverse reactions was 13% among patients treated with 100 mg ADDYI at bedtime and 6% among patients treated with placebo. Table 1 displays the most common adverse reactions leading to discontinuation in four trials of premenopausal women with HSDD.

**Table 1: Adverse Reactions\* Leading to Discontinuation in Randomized, Double-blind, Placebo-controlled Trials in Premenopausal Women with HSDD**

	PLACEBO (N=1556)	ADDYI (N=1543)
Dizziness	0.1%	1.7%
Nausea	0.1%	1.2%
Insomnia	0.2%	1.1%
Somnolence	0.3%	1.1%
Anxiety	0.3%	1%

\*Adverse reactions leading to discontinuation of > 1% of patients receiving 100 mg ADDYI at bedtime and at a higher incidence than placebo-treated patients.

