### 23. Inclusion/Exclusion Criteria:

#### Inclusion:

- Female
- Between 21 and 74 years old
- Menstruating for pre-menopausal and not menstruating for at least 6 months for the post-menopausal women. **The FDA defines postmenopausal as:** 12 months of spontaneous amenorrhea or 6 months of spontaneous amenorrhea with serum FSH levels >40mIU/ml or 6 weeks postsurgical bilateral oophorectomy with or without hysterectomy (U.S. Department of Health and Human Services, 2003).  
**Premenopausal is defined as** the period in a woman's life preceding menopause.
- DSM-5 diagnosis of hypoactive sexual desire disorder (HSDD) (also called disorder in sexual thoughts or interests)

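### The only between-arm safety criterion takes all HSDD participants together, and no adverse-event results by menopausal status are planned

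*Combined protocol and SAP*

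**What the plan says.** The trial's one between-arm safety statement is the last sentence of Section 11 (Statistical Hypotheses). It expects no related adverse events above mild severity on flibanserin "to a greater extent than PBO in HSDD participants". It gives no margin, test or interval, and no split by menopausal status.

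Sections 5 and 9 plan 60 premenopausal and 60 postmenopausal women. The inclusion criteria in Section 23 read "Between 21 and 74 years old". Section 5 describes the drug as approved for premenopausal women "but not FDA approved in postmenopausal women".

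The safety rates in Section 12 come from "placebo-controlled trials in premenopausal women with acquired, generalized HSDD". Of the women given 100 mg at bedtime it says "The age range was 18-56 years old with a mean age of 36 years old" and "The clinical trial population was generally healthy without significant comorbid medical conditions or concomitant medications". Among the rates given: "Serious adverse reactions were reported in 0.9% and 0.5% of ADDYI-treated patients and placebo-treated patients, respectively", and "The discontinuation rate due to adverse reactions was 13% among patients treated with 100 mg ADDYI at bedtime and 6% among patients treated with placebo".

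Menopausal status is a planned factor elsewhere. Aim 2 (Section 3) is built on it, and research question (b) in Section 11 compares the two groups, but on behavioural and brain changes only. Status is also a factor in the ANOVA of reaction times and ratings, and in the similar eye-tracking ANOVA. Section 28 records every adverse event with its severity, seriousness and relation to study drug, but describes no analysis by status.

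**The concern.** Section 12 already describes safety at length for premenopausal women, with 1543 of them on 100 mg at bedtime. It gives no rate for postmenopausal women, who are half of this sample. They are the group for whom a reader of this protocol would most want the trial's own safety results, and the plan does not commit to showing them separately.

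If the Section 11 criterion is judged on all participants and no excess is found, the natural reading is that neither group showed one. Two things could make that reading wrong. An excess confined to postmenopausal women is diluted by the premenopausal women, and the overall rate does not show where it arose. The precision of the overall figure also comes from twice as many women as the postmenopausal group contains.

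**Working it through.** **The plan's own figure.** There is none for safety. The only design calculation (Section 10: 120 women, effect size 0.14, 95% power) concerns a repeated-measures ANOVA interaction and has no bearing here.

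**Step 1: coverage, side by side.**

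| Item | Premenopausal | Postmenopausal |
|---|---|---|
| Planned number (Sections 5, 9) | 60 | 60 |
| Safety rates given in Section 12 | yes | none |
| Approval status stated in the protocol | approved | not approved |
| Own behavioural comparison (Section 11) | yes | yes |
| Own adverse-event comparison (Sections 11, 28) | none described | none described |

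**Step 2: cell size.** Section 5 gives 60 women per arm. With equal cells, 60 × 60/120 = 30 postmenopausal women take flibanserin. Randomization stratified by menopausal status is not described. If 60 of 120 women are assigned without stratification, the number is hypergeometric, with a central 95% range of 25 to 35.

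**Step 3: dilution.** Let *d* be an excess present only in postmenopausal women, with the same placebo rate in both groups (an assumption). The overall difference is *d* × (postmenopausal women on flibanserin)/60.
- 30 women: 30/60 = 0.50 *d*
- 25 women: 25/60 = 0.42 *d*
- 35 women: 35/60 = 0.58 *d*

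As an illustration, a 20-point excess would appear as 10 points (8.3 to 11.7).

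**Step 4: precision when no event of a given type is seen.** The exact upper limit is 1 − 0.05^(1/n) one-sided and 1 − 0.025^(1/n) two-sided.

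| Flibanserin women | One-sided 95% | Two-sided 95% |
|---|---|---|
| Whole arm, n = 60 | 4.9% | 6.0% |
| Postmenopausal, n = 30 | 9.5% | 11.6% |
| Postmenopausal, n = 25 | 11.3% | 13.7% |
| Postmenopausal, n = 35 | 8.2% | 10.0% |

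An event with a true 5% rate in 30 treated postmenopausal women is never seen with probability 0.95^30 = 0.21. At the 0.9% rate that Section 12 gives for serious reactions, the chance of seeing at least one is 1 − 0.991^60 = 42% in the whole arm and 1 − 0.991^30 = 24% in 30 women.

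**Step 5: what a test could show.** This step borrows the 24-week premenopausal rates of Section 12 purely as an assumption. The figures are the power of a two-sided Fisher exact test at 5%.

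| Assumed rates | 60 per arm | 30 per arm |
|---|---|---|
| Dizziness, 11.4% v 2.2% | 0.36 | 0.07 |
| Discontinuation for adverse reactions, 13% v 6% | 0.16 | 0.04 |

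Failing to find an excess is weak evidence in the whole trial and close to uninformative within one stratum. The stratum results should therefore be intervals, not tests.

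**The case against.** A reader might infer that the protocol already draws an overstated safety conclusion for postmenopausal women. It does not. The Section 11 sentence is a prospective criterion, and any overstatement could arise only in a later report.

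A reader might also infer that pooling is the specified method. It is not: no safety test, estimator or tabulation rule is stated, and the combined comparison is inferred from a population named only by diagnosis and from the lack of any subgroup safety analysis. Sections 7 and 19 could not be read and might bear on this.

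Nor is Section 12 in error. Its rates are openly labelled premenopausal, and nothing applies them to postmenopausal women, so a further disclaimer there would mostly repeat what is already said. The age range follows the account of the four 100 mg trials and may not cover the fifth, which enters the appendicitis and accidental-injury figures. The documents also do not show that postmenopausal safety data are lacking elsewhere, only that this protocol gives none.

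Two further points have force. Section 23 excludes unstable illness, any cancer history, hepatic impairment and interacting medication, which narrows the contrast with the healthy source population. And since status and all adverse events are recorded, a split table could be made at any time. The zero-event limits describe one arm, whereas the criterion concerns an excess over placebo; they show relative precision and do not test the criterion.

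What remains is that a table that could be made is not a table that is planned. The plan separates the groups for behaviour and eye tracking but not for safety.

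**Conclusion.** The point holds as a gap in planned reporting. The only between-arm safety criterion covers all HSDD participants, and no section that could be read plans adverse events by menopausal status, although the protocol gives no safety rate for half its sample.

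Read as covering both groups, a finding of no excess would hide roughly half of any excess confined to postmenopausal women. It would also suggest about twice the precision available for them: with zero events, an upper limit of 4.9% instead of 9.5% (8.2% to 11.3% for 35 to 25 women). The size rests on 60 women per arm, near-equal cells and, for the dilution, equal placebo rates in the two groups.

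The primary EEG analysis is unaffected. The change is worth making because it is cheap and alters what the trial can say about safety in postmenopausal women.

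**What to change.** At the safety criterion in Section 11, add a planned table of adverse events by arm within premenopausal and postmenopausal women. Its rows should be any event, events of more than mild severity, related events, and events leading to stopping tablets. Give exact 95% intervals for the arm difference in each stratum, and name the interval method. Specify no stratum-level significance tests and no stratum-level declarations of no excess. State that any safety statement about postmenopausal women will be limited to that stratum's interval.

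Do not compare the premenopausal stratum with the Section 12 rates. Those come from 24-week trials and this trial lasts 8 weeks.

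The cost is one table and a sentence or two. Status is fixed at entry and adverse events are already recorded, so no extra data, visits or participants are needed. The downside is wide intervals in each stratum and a less favourable-looking bound for postmenopausal women, which is the precision the trial actually has.
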